4.5 Final Study Assessment

Final study assessment will occur at the time of discharge or transfer. The following information will be collected:

1. Physical examination, including actual weight
2. Respiratory assessment (Section 8.2.2.3))
3. Concomitant medications of special interest (Section 6.5.1)
4. Echocardiogram and cardiac catheterization reports, if performed per local standard of care on the day of discharge or transfer or up to 2 days prior.
5. Global rank (Section 8.2.2.4)
6. Discharge information
 - A. Discharge or transfer
 - B. Death
 - C. Duration of hospitalization
7. Record if treatment for ROP was required

5 STUDY POPULATION

5.1 Participant Inclusion Criteria

To be eligible to participate in this study, an individual must meet all of the following criteria:

1. Documented informed consent from parent or guardian, prior to study procedures
2. < 29 weeks gestational age at birth
3. 32-44 weeks postmenstrual age
4. Receiving respiratory support at enrollment:
 - o If 32 0/7–35 6/7 weeks postmenstrual age: mechanical ventilation (high frequency or conventional)
 - o If 36 0/7–44 6/7 weeks postmenstrual age: mechanical ventilation (high frequency or conventional) OR continuous positive airway pressure (CPAP)

Note:

- o Criteria 3 and 4 define severe BPD for the purposes of this study
- o CPAP is defined as any of the following:
 - Nasal cannula > 2 liters per minute (LPM)
 - Nasal continuous positive airway pressure (NCPAP)
 - Nasal intermittent positive pressure ventilation (NIPPV)
 - Noninvasive neurally adjusted ventilatory assist (NAVA)
 - Any other device designed to provide positive pressure through a nasal device (e.g., RAM cannula, etc.)

5.2 Participant Exclusion Criteria

An individual who meets any of the following criteria will be excluded from participation in this study:

1. Previous enrollment and dosing in this study, protocol number (NHLBI-2019-SIL), “Safety of Sildenafil in Premature Infants with Severe Bronchopulmonary Dysplasia (BPD)”
2. Previous exposure to sildenafil within 7 days prior to randomization*
3. Previous exposure to vasopressors within 24 hours prior to randomization*
4. Previous exposure to inhaled nitric oxide within 24 hours prior to randomization*
5. Previous exposure to milrinone within 24 hours prior to randomization*
6. Evidence of pulmonary hypertension or moderate/large patent ductus arteriosus (PDA) on the most recent echocardiogram performed within 14 days prior to randomization
7. Known major congenital heart defect requiring medical or surgical intervention in the neonatal period
8. Known allergy to sildenafil
9. Known sickle cell disease

10. Aspartate aminotransferase (AST) > 225 U/L < 72 hours prior to randomization
11. Alanine aminotransferase (ALT) > 150 U/L < 72 hours prior to randomization
12. Any condition that would make the participant, in the opinion of the investigator, unsuitable for the study.

**Participant will be reassessed prior to dosing to reconfirm eligibility criteria.*

Note: Exclusion from participation due to enrollment in other clinical trials, including IND trials, will be left to the judgement of the site principal investigator (PI). Investigator judgement should consider the safety of the participant.

5.3 Strategies for Recruitment and Retention

The study will include up to 120 premature infants (< 29 weeks gestation) with severe BPD (will screen approximately 600 infants). Potential subjects will be identified in the NICU at participating sites. Due to the nature of the condition, a minority population is intrinsically overrepresented (minority population represents 30-40% of infants with BPD; <https://www.marchofdimes.org/peristats>). Therefore, the study team does not anticipate difficulty with inclusion of individuals commonly underrepresented in research studies.

Sites were selected based on prior participation in infant trials. Selected sites have research teams with extensive experience interacting with and enrolling the target population. Prior to and during the enrollment period for the study, sites will participate in conference calls to discuss recruitment and retention plans, including strategies for building rapport, increasing awareness, and enrolling the study population.

Study staff will remain in frequent contact with patients/parents to ensure that the follow-up data are collected pre the protocol schedule.

5.4 Treatment Assignment Procedures

5.4.1 Randomization Procedures

Randomization will occur on Day -1 among participants who satisfy all eligibility criteria. Participants will be centrally randomized via the EDC to maintain a 3:1 ratio within each cohort of sildenafil (n=30) to placebo (n=10). Participants from a multiple gestation will be randomized independently as they become eligible. If more than one infant from a multiple gestation is randomized, the sibling relationship between participants will be collected in the eCRF.

Reasons for premature discontinuation will be noted on the electronic case report form (eCRF). A randomized participant who prematurely discontinues from the study prior to receiving 7 days of study drug may be replaced with a new participant who will receive the same randomization assignment. Replacement will not be allowed if the reason for premature discontinuation is related to study drug (Safety Medical Monitor deems the event relationship as Possible, Probable, or Definite). The randomization process will not determine if an IV or enteral dose is used. Route of administration, IV or enteral, will

be left to investigator discretion. Participants should not have an IV placed specifically for study drug administration alone. However, if an investigator deems that a second IV would optimize the safe administration of other medications or fluids while the participant is receiving the study drug, then an additional IV is permissible. If the participant does not have an IV or if the clinical team elects to use enteral dosing, then the dose of study drug will be twice that of the IV dosing (from the product label). Infants may transition from enteral to IV sildenafil (and vice versa) throughout the duration of the study per the investigator's determination. Placebo will be administered either enterally or IV in the same manner.

Study randomization codes and replacement codes for all cohorts will be generated and uploaded prior to the enrollment of the first participant. One sequential dosing cohort will be available at a time for assignment. Subsequent cohort slots will only become available after completion of safety reviews. Unblinded results will only be shared with blinded members of the study team following database lock. Any unplanned unblinding of individual or treatment group-level data will be reported to the study PI. Unplanned unblinding will be reported to NHLBI Program Officer and the DSMB.

5.4.2 *Masking Procedures – Enteral Dosing*

Infants randomized to the placebo treatment group and receiving enteral study drug will receive the equivalent volume of dextrose 5% appropriate for enteral use. Staff accessing participant outcomes will be masked to treatment. Because prepared enteral sildenafil and placebo are visually slightly different, the pharmacy at each site will prepare and dispense the study drug into appropriate sized syringes in a masked manner (e.g., amber syringe, syringe overlay, etc.) in order to maintain masking of staff. Unmasking procedures are described in detail in the Manual of Procedures (MOP).

5.5 Participant Withdrawal or Discontinuation from Study Procedures/Intervention

5.5.1 *Reasons for Participant Withdrawal or Discontinuation from Study Procedures/Intervention*

The participant's parent or guardian may withdraw an infant from participation in the study at any time. Parents or guardians can choose to have infant discontinue study drug and continue to be followed or they can withdraw consent for further participation at any time.

The site investigator may choose to suspend study drug dosing once for up to 48 hours for any reason. If study drug is resumed by the site investigator, the dose and interval of the study drug will be the same as the prior dose. If applicable, subsequent doses will follow the dose escalation or weaning schedule as specified in section 6.1. If study drug is suspended for > 48 hours, the study drug administration will be discontinued and the participant will proceed directly into the safety follow-up period, during which all remaining assessments will be collected. If study drug is suspended for > 48 hours for a documented safety concern, the suspension will not be considered a protocol deviation.

The site investigator will withdraw a participant from receiving further study interventions, including study drug administration, and the participant will enter the 28-day safety-monitoring period if any of the following occur:

- During the course of the study, the participant meets safety-related criteria that would have led to initial exclusion from study participation (i.e., ALT > 150 U/L, AST > 225 U/L, or infant started on vasopressor or inhaled nitric oxide [Section 5.2]).
- Any clinically significant AE (e.g., hypotension) that is deemed by the site investigator to require discontinuation of study drug (see Section 9.5.3 for the definition of hypotension).
- Unmasking of the participant treatment occurs. All unmasking events should be recorded on a protocol deviation form in the EDC system within 24 hours of the unmasking. The decision to unmask will be made in consultation with the medical monitor.

Before discontinuing a participant from the study drug, the site investigator must contact the medical monitor or study PI, except in emergencies. All participants who have study drug suspended will continue to be in the study and complete all remaining study procedures in the safety follow-up period.

5.5.2 Handling of Participant Withdrawals from Study or Participant Discontinuation of Study Intervention

A randomized participant (Section 5.4.1) who prematurely discontinues from the study prior to receiving 7 days of study drug may be replaced with a new participant who will receive the same randomization assignment. Replacement will not be allowed if the reason for premature discontinuation is related to study drug (i.e., Safety Medical Monitor deems the event relationship as Possible, Probable, or Definite).

Participants who are prematurely discontinued from receiving study drug for any reason will be followed for 28 days after last study drug dose for safety monitoring, and will have final study assessments collected.

Reasons for participant withdrawal of consent or discontinuation from study drug will be appropriately documented by the site and captured in the appropriate eCRF, as instructed in the study eCRF Instructions provided to sites.

The participant's parent or guardian is not obligated to state the reason for withdrawal. The reasons for withdrawal, or decision not to provide a reason, must be documented by the investigator on the completion/withdrawal section of the corresponding eCRF. Participants/guardians who withdraw consent will not have any additional data entered in the EDC system.

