4. MAP
 - A. All MAP values obtained 24 hours after the first dose of study drug regardless of administration route.
 - B. MAP values will be obtained at a minimum at the following time points
 - i. Prior to the first dose of study drug or dose escalation: 2 hours (\pm 5 minutes), 1 hour (\pm 5 minutes), and 15 minutes (\pm 5 minutes)
 - ii. If administration route is IV:
 - a. During and following the first dose of study drug or dose escalation: MAP at start of infusion, every 15 minutes (\pm 5 minutes) during infusion, at end of infusion (inclusive of flush) (\pm 5 minutes), at 15 and 30 minutes (\pm 5 minutes) after end of infusion, hourly (\pm 15 minutes) for 4 hours, and once in the remaining 2 hours prior to the next dose.
 - b. For subsequent IV doses, the lowest valid MAP value should be recorded daily while on study drug.
 - iii. If the administration route is enteral:
 - a. During and following the first dose of study drug or dose escalation: MAP at start of enteral administration, then every 15 minutes (\pm 5 minutes) for 90 minutes (1.5 hours), then every 30 minutes (\pm 5 minutes) for 60 minutes (1 hour), then hourly (\pm 15 minutes) for 4 hours, then once in the remaining 2 hours prior to the next dose.
 - b. For subsequent enteral doses, the lowest valid MAP value should be recorded daily while on study drug.
5. Respiratory assessment, daily (Section 8.2.2.3)
6. Laboratory evaluations, at least once every 2 weeks (Section 8.2).
7. Echocardiograms and cardiac catheterization reports, if performed per local standard of care
8. PK sampling (after Day 7 [Section 8.2.2.1])
9. Adverse events (Section 9.3)

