6 STUDY INTERVENTION

6.1 Study Product Description

In the US, sildenafil, in both IV and for oral suspension, has been approved for use in other populations and for other indications by the FDA¹.

Study dosing and escalation are described in Table 3. Refer to Section 6.1.3 for study drug packaging and labeling.

Table 3 Number of Participants (N) and Dosing Scheme

Cohort ¹	Treatment Group		Sildenafil Dosing ² (mg/kg q 8 hours)		Total (N)
	Placebo (N)	Sildenafil (N)	IV	Enteral	
1	10	30	0.5	1	40
2	10	30	1	2	40
3	10	30	2	4	40

Abbreviations: IV, intravenous; N, number of participants; q, every

1 Participants will be enrolled into cohorts sequentially (i.e., Cohort 1 then Cohort 2 then Cohort 3) based on safety.

2 Route of administration, IV or enteral, is left to investigator discretion.

Dose escalations for each sequential cohort will proceed as summarized in Table 4. DSMB safety review (Section 10) will be required prior to enrolling the next cohort.

Table 4 Dose Escalations for Each Sequential Cohort

	Study Days (Dose Numbers)							
	1-2 (1-6)	3-4 (7-12)	5-6 (13-18)	7-8 (19-24)	9-10 (25-30)	11-12 (31-36)	13-14 (37-42)	15 + (43 +)
Sildenafil Dose (mg/kg)								
Cohort 1								
IV	0.25	0.5	0.5	0.5	0.5	0.5	0.5	0.5
Enteral	0.5	1	1	1	1	1	1	1
Cohort 2								
IV	0.25	0.5	0.75	1	1	1	1	1
Enteral	0.5	1	1.5	2	2	2	2	2
Cohort 3								
IV	0.25	0.5	0.75	1	1.5	1.75	2	2
Enteral	0.5	1	1.5	2	3	3.5	4	4

Abbreviation: IV, intravenous

Dose escalation will occur if the infant is:

1. Receiving exogenous oxygen or respiratory support (nasal cannula or positive pressure from any device); and
2. AST < 225 U/L and ALT < 150 U/L at last check (within 14 days) prior and closest to dose increase.

An infant will meet respiratory criteria for dose escalation only if the infant is receiving exogenous oxygen or respiratory support (nasal cannula or positive pressure from any device) for at least 12 hours before the dose escalation. Infants who do not initially qualify for escalation should be reevaluated daily to ascertain whether they meet these criteria, and escalation must occur within 24 hours of an infant meeting all dose escalation criteria (respiratory and laboratory). If escalation does not occur within this timeframe, then a protocol deviation must be recorded.

Adjusting dose for weight

The actual weight should be reviewed weekly (plus or minus one day, Section 4.2) and the dose of the study drug may be adjusted.

Weaning Period Schedule

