8 STUDY PROCEDURES/EVALUATIONS

8.1 Study Procedures/Evaluations

- A focused medical history of the participant will be extracted from the medical record.
- Concomitant medication information including name, route of administration, and dose will be extracted from the medical record.
- Physical examination including the vital signs (MAP) listed under the study schedule will be extracted from the medical record.
- Echocardiogram images will be uploaded for central review and interpretation at the coordinating center.
- Echocardiogram dates and reports will be collected in the EDC.
- Cardiac catheterization dates and reports will be collected in the EDC.
- Biological specimen collection will be performed per local procedures. See the MOP for further detail about biological specimen handling, storage, and shipping.
- Respiratory assessments will be extracted from the medical record (see Section 8.2.2.3 for more details).
- Discharge information will be extracted from the medical record.
- Protocol-specified MAP values will be obtained per local procedures.
- Blood pressure will be determined using MAP. For each participant, MAPs will be taken as noted in Section 4.2. Mean arterial pressure will be measured using an appropriate size cuff or with an intra-arterial placed catheter that measures continuous blood pressure.

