12.2 Sample Size Considerations

The sample size of 30 (sildenafil) in each dose group is sufficient to estimate hypotension incidence with sufficient precision. Table 8 provides widths for 95% Wilson confidence intervals in the dose groups of size 30 and the total sildenafil treatment cohort of 90 with different incidence rates. If hypotension occurs with an incidence rate of 0.05, it has a 78% chance of being observed at least once in a dose group and a 99% chance of being observed at least once in the total sildenafil cohort.

Table 8 Widths for 95% Wilson Confidence Intervals

N = 30			N = 90		
Rate	Width	95% CI	Rate	Width	95% CI
0.1	0.22	0.04-0.26	0.1	0.13	0.05-0.18
0.2	0.28	0.10-0.37	0.2	0.16	0.13-0.29
0.3	0.31	0.17-0.48	0.3	0.19	0.22-0.40

Abbreviations: CI, confidence interval; N, number of participants

Populations for Analysis

Intention to Treat (ITT) Population: Participants whose parent or guardian signs informed consent and are randomized.

Per Protocol (PP) Population: Participants who receive at least 7 days of study medication within 9 days (to allow for one pause in medication administration for up to 48 hours).

Safety Population: Participants who receive at least 1 dose of study medication.

PK Population: All participants who have at least one interpretable PK sample.

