12.4 Final Analysis Plan

General Analysis Conventions

A comprehensive overview of planned statistical analyses will be provided in a separated statistical analysis plan.

Analysis results will be presented by placebo versus sildenafil, overall and by dose cohort. Data from participants assigned to placebo across cohorts will be pooled in result presentations.

Descriptive statistics such as number of observations, mean, median, standard deviation, minimum and maximum will be presented by treatment groups for continuous variables (such as age, weight, etc.). Other descriptive statistics such as counts, proportions, and/or percentages will be presented by group to summarize discrete variables (such as race, sex, etc.).

Participant Disposition and Study Drug Exposure

Study disposition, demographic and baseline characteristics, and study medication exposure will be summarized for the ITT Population. Study drug administration will be summarized by route (IV vs enteral), number of days of dosing, and reasons for final discontinuation of study drug.

Demographic and baseline characteristics

Demographic and baseline characteristics will include race, age, sex, and selected clinical variables recorded prior to initiation of study drug.

Safety

The primary safety endpoint is number and percent of hypotension events and will be summarized for the PP and Safety Population.

Serious adverse events will be presented overall and by each Medical Dictionary for Regulatory Activities (MedDRA) system organ class and preferred term. Severity and relationship to sildenafil or placebo will be provided.

Events of special interest will be presented overall and summarized by participant characteristics.

Prior and concomitant medications will be summarized by World Health Organization (WHO) drug class.

Laboratory data, including change from baseline, will be tabulated by treatment groups.

PK Analysis Plan

A comprehensive overview of planned PK analyses will be provided in a separated PK analysis plan.

Pharmacokinetic parameters will be estimated by population PK approach using nonlinear mixed effects modeling in NONMEM. The influence of covariates on PK parameters will be explored.

Biomarkers

We will relate the concentration of biomarkers (Section 8.2) to the development of and severity of PH in participants exposed to placebo.

Preliminary Effectiveness

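### Protocol 4.2 does not require the timed MAP readings when study drug restarts at the full prior dose after a pause of 24 to 48 hours

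*Combined protocol and SAP*

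**What the plan says.** **Pause and restart (5.5.1).** The site investigator may suspend dosing once, for any reason, for up to 48 hours. If dosing resumes, "the dose and interval of the study drug will be the same as the prior dose", and later doses rejoin the escalation or weaning schedule where that applies. Starting a vasopressor, or hypotension that the investigator judges to require stopping the drug, leads to withdrawal instead.

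**MAP schedule (4.2, item 4.B).** For IV dosing: "During and following the first dose of study drug or dose escalation: MAP at start of infusion, every 15 minutes", and so on until shortly before the next dose. The enteral schedule and the three pre-dose readings have the same trigger. Otherwise, "For subsequent IV doses, the lowest valid MAP value should be recorded daily while on study drug"; the enteral rule is the same. These are stated as minimum requirements.

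**Other sections.** Section 8.1 refers back: "For each participant, MAPs will be taken as noted in Section 4.2". Section 6.2 and Table 6 add no trigger for a restart. In weaning, 4.3 asks only for the lowest MAP on the last day.

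**Escalation (6.1).** "Dose escalations for each sequential cohort will proceed as summarized in Table 4". The steps there run from a doubling (0.25 to 0.5 mg/kg IV) down to 14% (1.75 to 2 mg/kg IV, Cohort 3).

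**Analysis (12.2, 12.4).** The per-protocol definition is framed "to allow for one pause in medication administration for up to 48 hours". "The primary safety endpoint is number and percent of hypotension events and will be summarized for the PP and Safety Population".

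**The concern.** The protocol requires close MAP monitoring when exposure steps up, even for a 14% step in dose. A restart after a day or two is also a step up: much of the drug has probably cleared, and exposure returns in a single dose to a level first reached by titration. In Cohort 3 that dose can be 2 mg/kg IV, eight times the monitored starting dose (2/0.25).

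The pause may itself have followed hypotension. Under 6.2 a dose is stopped for clinically significant hypotension, and the clinical team then decides whether to continue. Hypotension treated with a fluid bolus meets the primary endpoint but does not by itself force withdrawal, so such an infant can restart at the full prior dose with no timed readings required.

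The primary endpoint is low pressure that a physician decides to treat, so it must first be noticed. If restart monitoring is left to local practice, safety cover and detection can differ between sites.

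**Working it through.** **1. Does any rule cover a restart?** A restart at an unchanged dose is not a first dose and not an escalation. Under 4.2 it falls to the daily-lowest rule, and 4.3, 6.2, 8.1 and Table 6 add nothing. The timed series is therefore not required.

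**2. Readings required at an escalation.**
- IV: 3 before + 1 at start + 4 or 5 at 15-minute intervals + 1 at end + 2 after + 4 hourly + 1 before the next dose = 16 or 17.
- Enteral: 3 + 1 + 6 + 2 + 4 + 1 = 17.
- Restart: 0 timed readings; the day's lowest MAP is still recorded.

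**3. Half-life (assumed).** Section 2.2 gives clearance and volume but no half-life.
- Sildenafil, central volume only: ln 2 × 116/27.8 = 2.9 h. This is a lower bound, because the model has two compartments.
- N-desmethylsildenafil (DMS): ln 2 × 1670/135 = 8.6 h.
- Range used: 3 to 12 h.

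**4. Drug remaining after the last dose.**
- 24 h: 2^(−24/3) = 0.4% to 2^(−24/12) = 25%.
- 48 h: at most 2^(−48/12) = 6.25%.

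**5. Rise in 8-hour exposure.** One compartment, linear, bolus every 8 h, from steady state, with r = 2^(−8/half-life). Exposure is 8-hour AUC as a fraction of its steady-state value; T is hours since the last dose.
- Last 8 h before restart: r^((T−8)/8)
- First 8 h after restart: r^(T/8) + 1 − r
- Escalation by factor s, first 8 h: r + s(1 − r)

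| Half-life | r | Restart at 24 h | Restart at 48 h | s = 2.0 | s = 2/1.75 = 1.143 |
|---|---|---|---|---|---|
| 3 h | 0.157 | 0.846/0.0248 = ×34 | above ×8000 | ×1.84 | ×1.12 |
| 6 h | 0.397 | 0.666/0.157 = ×4.2 | 0.607/0.0098 = ×62 | ×1.60 | ×1.09 |
| 12 h | 0.630 | 0.620/0.397 = ×1.56 | 0.433/0.0992 = ×4.36 | ×1.37 | ×1.05 |

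In every row the restart exceeds every escalation step. With a 60-minute infusion in place of a bolus, the restart rises are ×1.49 to ×30 at 24 h and ×4.1 or more at 48 h; the conclusion is the same.

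**6. Level reached.** The after-restart values lie between 0.433 (12 h half-life, 48 h) and 0.846 (3 h half-life, 24 h). The first 8 hours thus reach 43% to 85% of the exposure before the pause.

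**7. The plan's own figures.** None addresses a restart. The detection probabilities in 12.2 reproduce (1 − 0.95^30 = 78.5%; 1 − 0.95^90 = 99.0%) and do not depend on this point.

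**The case against.** The best defence is that intensive MAP belongs at dose levels the infant has never had. An escalation reaches such a level; a restart returns to one already received. That is a coherent design choice, and it is why this is a suggested improvement and not an error.

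Four further points limit the concern:
- Section 4.2 sets a minimum. The daily lowest MAP will capture a measured drop if it is that day's lowest value, and the infants are NICU inpatients. The Manual of Procedures, which is not among the documents, may say more.
- The large ratios (×34 and above) come from a denominator close to zero after washout and should carry no weight. The useful figures are the smallest ones. At a 12-hour half-life the 24-hour restart is only modestly above a doubling, ×1.56 against ×1.37.
- The metabolite is not modelled separately, and the 24-hour cut-off is a choice made here; the protocol has none.
- Other protections exist: the 60-minute infusion with flush, stopping a dose for hypotension, withdrawal if a vasopressor is started, and the DSMB triggers in 9.5.2.

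What stands is that a guaranteed reading frequency applies to a 14% step and not to a larger rise in exposure at restart.

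A reader might also infer that a first IV dose after enteral dosing goes unmonitored, since "Infants may transition from enteral to IV sildenafil (and vice versa) throughout the duration of the study". The documents do not establish this. The route-by-route layout of 4.2 favours counting a first IV dose as a first dose, although item 4.A can be read the other way. At the 2:1 dose, Table 1 gives a combined AUC ratio of 3581/2941 = 1.22 (parent 3157/1825 = 1.73). This is a matter of wording only.

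**Conclusion.** The gap is real and modest. After a pause of 24 to 48 hours, drug can restart at the full prior dose with no timed MAP readings required. Under an assumed half-life of 3 to 12 hours, 8-hour exposure rises at least ×1.56 at 24 hours and ×4.4 at 48 hours, against ×1.05 to ×1.84 at the escalation steps; at each half-life the restart is the larger. These figures rest on a one-compartment linear model and on dosing at steady state before the pause.

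Three stronger readings are not supported:
- That restarts are unmonitored: the daily lowest MAP is required, and sites may do more.
- That the arms are compared unfairly, or that a stated incidence or precision figure changes: both arms follow the same schedule, and nothing in 12.2 depends on it.
- That many infants are affected: the per-protocol definition allows for a pause but says nothing about how often one occurs. The number is unknown.

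The case for acting is patient safety and more even detection of the primary endpoint, at low cost.

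**What to change.** In 4.2, item 4.B, apply the timed MAP schedule also to the first dose given 24 hours or more after the last dose (at least two missed doses at 8-hour intervals). Put the same rule in 4.3 for dosing that resumes during weaning. Leave the restart dose in 5.5.1 as it is; whether to lower it after hypotension is a clinical trade-off for the clinical team and the DSMB.

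Optionally, state in 4.2 that the first dose under the IV schedule includes the first IV dose after enteral dosing. This is a clarification and the fix does not depend on it.

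Cost: about 16 to 17 cuff or arterial-line readings per affected infant, and a short protocol and eCRF amendment, with IRB handling, across approximately 30 sites. No extra participants, visits or blood are needed, and the 168 hours at target dose before PK sampling is unaffected.
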